6. INVESTIGATIONAL PRODUCT(S)

All investigational products to be used in this study have been manufactured, packaged and labeled by contract manufacturers for ABIVAX, according to GMP standards and are supplied to investigators free of charge.

6.1. Description of investigational treatment

The study treatment that will be administrated to subjects enrolled in this Phase Ib study consists of capsules containing ABX464 given orally once daily for 28 days (Cohort 1&2) or for 84 days (Cohort 3).

6.2. Description of investigational Product

6.2.1. Active investigational product (ABX464)

The ABX464 investigational medicinal product (IMP) is a hard gelatin capsule intended for oral administration.

For the proposed clinical trial, the IMP consists of size 00 capsules containing 50 mg of ABX464 drug substance in the form of a granulate prepared with a number of common excipients (microcrystalline cellulose, polyvinylpyrrolidone, magnesium stearate and colloidal silica). It is supplied in high-density polyethylene bottles closed with high-density screw caps.

ABX464 will be manufactured by SEPS Pharma (Belgium).

SEPS Pharma CTM
[name]
9052 Gent Belgium

Primary packaging labelling as well as Qualified Person release of the IMP are performed at the following site:

SODIA
[name]
51 000 REIMS

The study drug has to be stored at ambient temperature (< 25°C). The capsule or combination of capsules to be used depends on the dose-level to be administered as per the clinical study protocol.

6.3. Administration and Dosing

6.3.1. Administration of the investigational product

Subjects will be dosed with a daily dose of 150 mg of ABX464 (Cohort 1) or of 50 mg ABX464 (Cohorts 2&3). ABX464 will be administered using 50 mg capsules. Subjects will be orally dosed in fed condition (regular breakfast) with 240 mL of water.

A subject diary, in which the subject should report the number of capsules taken and the intake time, will be given to the subject at baseline. Moreover, this diary will enable the subject to report also potential discomfort or side effects s/he could experience.

6.3.2. Guidelines for treatment postponement and dose modifications

No intra-subject dose escalation/dose adjustment are allowed.

6.4. Method of Assigning Subjects to Treatment Arms

All subjects will be assigned a unique and incremental subject identification (ID) number. Subject IDs will be unique (i.e. reallocation of the ID will not be permitted). The format will be a seven-digit number as follows: ABX-country/site number (4 digits) – subject number (3 digits). The latter 3-digit subject number will be assigned according to the subject's order of inclusion in the center.

Initial enrollment will occur into Cohort 1, and subsequently into Cohort 2 & 3.

Potential patients prematurely withdrawn from the study for any reason will be replaced. In all cases, subject should return his/her used and unused bottles at each study visit for a compliance check.

6.5. Packaging

The IMP consists in hard gelatin, powder-filled capsules (size 00) containing 50 mg of ABX464, supplied in high-density polyethylene bottles closed with high-density screw caps.

6.6. Storage

ABX464 capsules will be shipped to the investigational site at ambient temperature. ABX464 capsules should not be stored above 25°C. DO NOT FREEZE OR REFRIGERATE.

The IMP should not be used beyond the expiration date. Drug supplies are to be stored in a secure, limited-access location under the storage conditions required by GCP/GMP guidelines.

6.7. Product Accountability

An accurate and current accounting of the dispensing and return of IMP(s) will be maintained on an ongoing basis by the pharmacist and a member of the study site staff in the Accountability Log and case report form and will be verified by the study's monitor.

6.8. Prior and Concomitant Medication

6.8.1. Background and allowed concomitant treatment

All HIV positive Subjects must be receiving treatment with a combination antiretroviral regimen.

6.8.2. Prohibited prior or concurrent medications

Prohibited prior or concomitant treatments:

Following medications are prohibited potentially prior to baseline and during the course of the study.

- Medications prohibited within 3 months prior to baseline and during the whole course of the study
 - Immunomodulators or immunosuppressive drugs (such as IL-2, IL-7, intravenous immunoglobulin- IVIG, IFN γ , or Imiquimod, IVIG, IFN γ , or Imiquimod);
 - Any investigational or non-registered product.
- Medications prohibited within 1 month prior to baseline and during the whole course of the study
 - HIV negative Subjects should not be taking antiretroviral pre-exposure prophylaxis (PrEP) or have completed a course of antiretroviral post exposure prophylaxis (PEP) within one month of the enrollment visit.
- Medications prohibited within one week prior to baseline and during the whole course of the study
 - Heparin, including Lovenox $^{\circ}$ (enoxaparin sodium);
 - Warfarin;
 - Plavix $^{\circ}$ (clopidogrel bisulfate);
 - Any other drugs that are associated with increased likelihood of bleeding following mucosal biopsy (e.g., daily high dose aspirin (> than 81 mg), NSAIDs, or Pradaxa $^{\circ}$);
 - Rectally administered medications (including over-the-counter products);
 - Multiple dose dexamethasone.
- Medications prohibited during the whole course of the study
 - Drugs that could interact either with ABX464 should be avoided especially the CYP1A2 substrates or inducers (cf. Appendix#2). The following CYP1A2 substrates or inducers with a narrow therapeutic margin are prohibited during the whole course of the study (clozapine, theophylline, ropinirol, warfarin and methadone).

Potential concomitant medications should be kept at constant dose during the course of the study and properly reported in the medical file of the subject and the eCRF.

This information should include the name of the medication (international nonproprietary name), daily dosage, duration, indication and the time of last intake before all PK samplings.

7. SUBJECT COMPLETION AND WITHDRAWAL

7.1. Subject Completion

Treatment with ABX464 shall continue until Day 28 (Cohort 1&2) or Day 84 (Cohort 3), except if a subject fulfils a premature discontinuation criterion (defined below). After discontinuation of study product (End of Rx Visit; Day 28/84) subjects will return for two follow-up visits (FU Visit; Day 35/91 and EoS Visit; Day 56/112).

7.2. Premature trial discontinuation

A subject can be withdrawn at any time from the study for the following reasons:

- Investigator's decision;
- An Adverse Event or an intercurrent condition that preclude continuation of treatment;
 - Specifically, an increase $\geq 2.0 \times$ ULN in liver transaminases (AST/SGOT and/or ALT/SGPT), in alkaline phosphatase or in total bilirubin should be considered a treatment discontinuation criterion
- Major protocol violation;
- Subject's decision;
- Withdrawal of consent.

A subject who prematurely exits the study before Day 28 (Cohort 1&2) or Day 84 (Cohort 3) will be replaced (i.e. an additional subject will be randomized and receive the next treatment allocation).

7.3. Study Discontinuation

All subjects, regardless of the completion or premature discontinuation, should perform the End of Study Visit (EoS) according to the study flow-chart. In case a premature discontinuation this EoS visit should occur within the next two weeks after the last dosing and should include but depending on the subject willingness the PK evaluation and the sigmoidoscopy.

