Additional follow-up visit will occur 1 week (Day 35 / Day 91) and 1 month (End of study visit; Day 56 / Day 112) after stopping study product. During these two visits the subjects will undergo a physical examination and have blood (through PK) and rectal tissue samples collected at End of Study (EoS) visit only (Rectal tissue only for Cohorts 1 and 3).

The blood samples collected in this study will be used to characterize general safety, and in HIV infected subjects to monitor viral load and CD4+ counts, to quantify PK exposure to ABX464 and its metabolites, and blood samples collected will be used to assess systemic immunological effect of ABX464 and alteration of HIV reservoir.

Rectal biopsies will be collected 15 cm from the anal verge and will be used to quantify PK exposure in rectal tissue, to determine whether ABX464 alters gut associated lymphoid tissue (GALT) immunology, and to assess whether exposure to ABX464 alters HIV GALT reservoirs in the HIV-infected subjects or reduce the incidence or magnitude of HIV infection in rectal tissue from HIV-uninfected subjects. GALT HIV reservoirs (RNA and DNA) will be characterized using previously published techniques (4). Ex vivo / in vitro rectal explant challenge will also be performed using previously published techniques in which rectal biopsies are challenged with high titers of HIV-1_{BAL} and cumulative, weight adjusted HIV-1 p24 antigen is quantified in the explant supernatant (2). Additional studies of mucosal proteome, transcriptome, and microbiome will provide a comprehensive assessment of mucosal biology before and after exposure to ABX464.

The ABX464-005 study design is summarized below.

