3.2. Duration of study participation

From a subject standpoint, the study participation is defined as

- Two to four weeks of screening period;
- Four weeks (Cohorts 1 & 2) or twelve weeks (Cohort 3) as the treatment period (ABX464);
- Follow-up visits at 1 week and 4 weeks after cessation of study medication.

Overall, the minimal study duration will be approximately 70 days and up to 140 days depending on the subject Cohort.

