5. STUDY ASSESSMENTS AND PROCEDURES

5.1. Study Flow Chart

A detailed study flow chart (with all assessments) is displayed below.

Study procedures	Screening Visit	Baseline Visit	Control Visits	Day 28 / D56	End of Study treatment visit	FU visit	FuS visit Cohort 1&3	FuS visit Cohort 2
	Screening 21 ± 7 days	Baseline	Cohort 2 only ± 2 days	Cohort 3 only ± 2 days	28-Day (Cohort 1&2), 84-Day (Cohort 3) ± 2 days	FU visit 1-week post completion ± 2 days	FU visit 4 weeks post completion ± 7 days	FU visit 4 weeks post completion ± 7 days
Informed Consent	X	Day 1	Day 7, 14, 21	Day 28 / D56	Day 28 / Day 84	Day 35 / Day 91	Day 56 / Day 112	Day 56
Inclusion/Exclusion Criteria	X							
ECG	X	X			X		X	X
Adverse Event reporting	X	X	X	X	X	X	X	X
Concomitant medication checks and	X	X	X	X	X	X	X	X
Physical examination and vital signs	X	X	X	X	X	X	X	X
Hematology & Biochemistry	X	X						
Syphilis, HBV/HCV serology	X							
HIV-1 antibody serology #	X							
Urine and Rectal GC/CT (NAAT)	X				X	X	X	X
TNR & PT	X	Δ			Δ	Δ	Δ	Δ
HIV-1 viral load \$	X	X			X*	X	X	X
CD4+ and CD8+ counts \$	X	X			X*	X	X	X
Pharmacokinetics: Plasma and PBMC		0h, 0.5h, 1h, 1.5h, 2h, 4h, 6h and 8h	X*	X*	0h, 0.5h, 1h, 1.5h, 2h, 4h, 6h and 8h	X Trough	X Trough	X Trough
Flexible sigmoidoscopy for Rectal Biopsy		X			X*	X	X	X
- Explant infection #	X				X*	X	X	X
- MMC flow cytometry	X				X*	X	X	X
- Rectal microbiome	X				X*	X	X	X
- Rectal proteomics	X				X*	X	X	X
- Rectal transcriptomics	X				X*	X	X	X
- Rectal tissue pharmacokinetics	X				X*	X	X	X
- Rectal HIV Reservoir \$	X				X*	X	X	X
Blood samples for Immunology & Molecular assays		X			X*	X	X	X
- PBMC flow cytometry	X				X*	X	X	X
- Plasma SCAs \$	X				X*	X	X	X
- Plasma inflammatory markers	X				X*	X	X	X
Blood samples for HIV reservoir assays \$		X			X	X	X	X
- PBMC HIV reservoir \$	X				X	X	X	X

CT; Chlamydia trachomatis, GC; Neisseria gonorrhoea, HBV; hepatitis B virus, HCV; hepatitis C virus, INR; international normalized ratio, NAAT; nucleic acid amplification testing, MMC; mucosal mononuclear

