8.4. Time Period, and Frequency of Detecting AEs and SAEs

All AEs and SAEs occurring from the time a subject consents to participate in the study until 4 weeks after he or she has completed or discontinued the investigational product must be recorded in the subject's eCRF. Importantly, SAEs will have to be reported to ABIVAX or its designee within 24 hours of awareness of an SAE.

Legislative guidance requires also reporting any **related** SAEs to be reported after the subject finished the study if the investigator becomes aware of them.

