8.5. Recording AEs and SAEs

Severity of AEs will be assessed according to "Division of AIDS table for grading the severity of adult and pediatric adverse events", version 2.0 of November 2014.

Subjects will be asked to report all AEs as part of the procedures performed at each study visit. The site personnel will document all AEs in the subject's medical record. All AEs subsequently must be recorded in the appropriate eCRF sections.

The following points must be recorded for each event:

- A description of the event in medical terms, not as reported by the subject;
- Date of onset (start date);
- Date of resolution (stop date);
- The time of onset with respect to administering the investigational product;
- The severity of the sign/symptom or clinically significant abnormal laboratory value according to CTC AE Classification;
- The causal relationship between the investigational product and the occurrence of each AE. This will be assessed by each investigator using clinical judgment. Alternative causes, such as natural history of the underlying diseases, concomitant medications, other risk factors and the temporal relationship of the event to the investigational product will have to be considered. The causality of all AEs should be assessed by the investigator with the following question: Is there a reasonable possibility that the AE may have been caused by the investigational product? And answered "NO" (if not related) and "YES" (if related);
- Action taken regarding the investigational product:
 - No action;
 - Temporary discontinuation;
 - Permanent discontinuation;
- Subject's outcome:
 - Recovered without sequelae / resolved without sequelae;
 - Recovered with sequelae / resolved with sequelae;
 - Recovering/Resolving;
 - On-going;
 - Fatal (for SAEs only).

If in any one subject, the same AE occurs on several occasions, the AE in question must be documented and assessed anew each time.

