### 3.4 Study Timepoints

From a subject standpoint, the study participation is defined as

- Two to four weeks of screening period;
- Four weeks (Cohorts 1 & 2) or twelve weeks (Cohort 3) as the treatment period (ABX464);
- Follow-up visits at 1 week and 4 weeks after cessation of study medication.

Overall, the minimal study duration is approximately 70 days and up to 140 days depending on the subject Cohort.

Visits and visit windows are defined as follows:

Visit	Study Day	Window
-------	-----------	--------

Screening	-21	± 7 days
Baseline	1	
Control (Cohort 2 only)	7	± 2 days
Control (Cohort 2 only)	14	± 2 days
Control (Cohort 2 only)	21	± 2 days
Day 28 (Cohort 3 only)	28	± 2 days
End of Study Treatment (Cohort 1 & 2)	28	± 2 days
Follow-up (Cohort 1 & 2)	35	± 2 days
End of Study (Cohort 1 & 2)	56	± 7 days
Day 56 (Cohort 3 only)	56	± 2 days
End of Study Treatment (Cohort 3 only)	84	± 2 days
Follow-up (Cohort 3 only)	91	± 2 days
End of Study (Cohort 3 only)	112	± 7 days

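### Early stoppers have their last scheduled visit within 2 weeks of the last dose, but adverse events must be recorded for 4 weeks

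*Protocol*

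**What the plan says.** Protocol 7.3 asks every subject, completer or not, to have an EoS visit according to the flow chart. It then sets a special rule for those who stop early: "In case a premature discontinuation this EoS visit should occur within the next two weeks after the last dosing". PK sampling and sigmoidoscopy at that visit depend on the subject's willingness.

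Protocol 8.4 sets the same recording period for everyone. AEs and SAEs occurring from consent "until 4 weeks after he or she has completed or discontinued the investigational product must be recorded" in the eCRF. On how events are elicited, Protocol 8.5 says: "Subjects will be asked to report all AEs as part of the procedures performed at each study visit".

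The general description of follow-up does not mention early stoppers. Protocol 3.2 lists "Follow-up visits at 1 week and 4 weeks after cessation of study medication", and 3.1.1 says much the same. Protocol 7.1 ties the two follow-up visits to fixed days: 35 and 56 for Cohorts 1 and 2, 91 and 112 for Cohort 3. The flow chart in Protocol 5.1 labels the EoS visit "FU visit 4 weeks post completion ± 7 days", and SAP 3.4 gives the windows by study day.

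SAP 11.4.1 classes events after the end of treatment as post-treatment-emergent. For an event still ongoing, it takes the end-of-study date as the stop date, or the last known visit date after early termination.

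**The concern.** The recording period names those who discontinue, but the visit that should close it is moved to its midpoint or earlier for exactly those subjects. After that visit the protocol schedules nothing. An event starting on, say, day 20 off drug is recorded only if the subject volunteers it.

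The reasons for stopping in Protocol 7.2 include an adverse event and raised liver tests, so early stoppers may be the subjects of most safety interest. They are replaced, but they stay in the Safety set after one dose and are tabulated beside completers who are nominally observed for 28 days off drug.

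Under SAP 11.4.1 the shortfall falls on the any-AE and post-treatment-emergent rows, not on the TEAE count. Protocol 9.3 is less clear-cut, since it also lists events after Day 28 as a TEAE period. The mean-duration summary is affected as well, because an event ongoing at an early last visit is cut off at that visit. Safety is a secondary objective, so this does not touch the primary PK endpoint.

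**Working it through.** **Inputs**
- Recording period after stopping drug: 4 weeks = 28 days (Protocol 8.4; 8.1 also gives 4 weeks).
- Early stopper's EoS visit: at most 14 days after the last dose (Protocol 7.3).
- Completer's EoS visit: Day 56 after a last dose on Day 28, or Day 112 after Day 84, with ±7 days (Protocol 5.1 and 5.3.8; SAP 3.4).
- End-of-treatment visit: ±2 days (SAP 3.4). The final dose is taken at that visit (Protocol 5.4.8 states this for Day 28; the same is assumed for Day 84).
- Duration of an event = stop date − start date + 1 (SAP 11.4.1).

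**Plan's own figure.** Protocol 3.2 gives participation of about 70 to 140 days. This is reproduced as 7 × (2 + 4 + 4) = 70 and 7 × (4 + 12 + 4) = 140. Also 56 − 28 = 28 and 112 − 84 = 28. A completer's nominal EoS visit therefore falls at the end of the recording period.

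**Days without scheduled questioning** = 28 − v, where v is the number of days from the last dose to the last scheduled contact.

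| Subject | v | Uncovered days |
|---|---|---|
| Early stopper, EoS on day 14 (latest allowed) | 14 | 14 (50%) |
| Early stopper, EoS on day 7 | 7 | 21 (75%) |
| Completer, nominal | 28 | 0 |
| Completer, −7 days counted from the last dose | 21 | 7 (25%) |
| Completer, study-day windows, Cohorts 1 and 2: Day 49 − Day 30 | 19 | 9 (32%) |
| Completer, study-day windows, Cohort 3: Day 105 − Day 86 | 19 | 9 (32%) |

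The early stopper's minimum gap exceeds the worst completer case by 14 − 9 = 5 days. The 1-week follow-up visit falls inside the first 14 days, so it does not reduce the gap.

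**Duration of an event that starts on the last dosing day and stays ongoing**
- Early stopper with no later visit: at most 14 + 1 = 15 days.
- Completer, nominal: 28 + 1 = 29 days.
- Completer, window from the last dose: 21 + 1 = 22 to 35 + 1 = 36 days.
- Completer, study-day windows: 19 + 1 = 20 to (63 − 26) + 1 = 38 days.

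**Remaining exposure.** Protocol 5.4.8 gives the metabolite a half-life of 90 to 110 h. Assuming first-order decay, the fraction left at day 14 (336 h) is 0.5^(336/90) = 0.075 to 0.5^(336/110) = 0.120. At day 28 (672 h) it is 0.006 to 0.014. Part of the uncovered period therefore still has some exposure.

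**The case against.** The strongest reply is that the 14-day figure depends on the 7.3 visit being the last contact, which the protocol does not state outright. Section 7.3 itself refers to the flow chart, where EoS is at 4 weeks, and 3.1.1 and 3.2 describe follow-up after stopping drug without restricting it to completers. This stands as a limit: the figure is conditional. But 7.3 is the only text written for early discontinuation. It moves the EoS visit rather than adding one, and the fixed days in 7.1 do not fit someone who stops on Day 10, for example. For subjects who leave the trial, 7.3 probably governs. For those who stop only the drug, the text is ambiguous.

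Second, the duty to record remains, and there are safeguards: significant laboratory abnormalities are followed to resolution (5.4.3), the AE period may be extended (8.1), related SAEs stay reportable (8.4), and subjects keep a diary (6.3.1). None of these schedules a check for new events, and the diary is not said to continue after dosing. The laboratory rule does largely cover known liver abnormalities, so what remains is new or late events.

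Third, the effect on the results is modest. The tables are descriptive, by non-randomised cohort, and no planned comparison sets early stoppers against completers. The duration example is an extreme case, and cutting off ongoing events also affects completers. This is fair and limits the weight of the point. Finally, subjects who withdraw consent cannot be contacted under any wording.

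**Conclusion.** The concern holds. If the early EoS visit is the last contact, at least 14 of the 28 recording days (50%) have no scheduled questioning, against 0 nominally for a completer and 7 to 9 at worst. The gap is in detection, not in the duty to record.

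This rests on reading 7.3 as replacing the 4-week visit for early stoppers. If 3.1.1 and 3.2 are meant to apply to them as well, the defect is that 7.3 does not say so. The documents give no early-stopping rate, so the number of subjects affected cannot be calculated and is probably small. It should be fixed because the correction is cheap and improves safety detection. It does not threaten the primary analysis. Confidence is medium because of the conflicting text.

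**What to change.** In Protocol 7.3, keep the visit within two weeks as an early-termination visit, with PK and sigmoidoscopy optional as now. Add one AE/SAE contact, by telephone or visit, at day 28 after the last dose (window 0 to +7 days) for every early stopper who has not withdrawn consent. Do laboratory tests or an ECG at that contact only if an earlier abnormality is unresolved or there is a clinical reason.

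In SAP 11.4.1, use the date of this contact as the last known date for ongoing events. State that events found at it count in the overall AE table, which Protocol 9.3 at present closes at EoS. A flow-chart footnote should show the contact, and a sentence in 7.3 should say whether subjects who stop only the drug also keep the 1-week visit.

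With the contact made on day 28, uncovered days fall to 28 − 28 = 0, and the example event gets 28 + 1 = 29 days, equal to the nominal completer.

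The cost is a few sentences across the two documents and one call or visit per early stopper, with no routine blood draw, ECG or biopsy. Some subjects may decline the extra contact, and it does not help those who withdraw consent.

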7.4. Screen and Baseline Failures

A subject is considered to be a baseline failure if the subject signs the informed consent but withdraws before the screening visit. All potential subjects who are screened for enrolment in this study will be listed on the Subject Screening Log/Identification List. Reasons for exclusion will be recorded for potential subjects who do not enter the study.

A subject who does not fulfil the randomization criteria at the end of the screening will be considered as screen failure. All subject data should be entered in the eCRF including the screen failure data.

Re-screening of a subjects is allowed but limited to rectal and urinary tract infection. In such a case the time frame for a re-screening is 1 month.

